14.5 Protocol Amendments

Any changes that affect patient safety or welfare will be submitted to the IRB/IEC and Regulatory Authority (where applicable) for approval prior to implementation. The Investigator and the Sponsor must approve all amendments. No amendment will be implemented until approved and signed by all parties. Exceptions to this are when the Investigator considers that the patient's safety is compromised.

Once the study has started, amendments should be made only in exceptional cases. The changes then become part of the study protocol.

14.6 IRB/IEC Approval and Reporting

The Investigator must obtain appropriate IRB/IEC approval prior to study initiation. A copy of the written approval from the IRB and a copy of the approved ICF should be sent to the Sponsor or its delegate. It is also necessary to submit a list of the IRB members (including their Institution affiliations, gender makeup, and occupations) or supply a statement from the IRB specifying that the membership complies with applicable regulations.

The study protocol, ICF, the IB, available safety information, patient recruitment procedures (e.g., advertisements), information about payments and compensation available to the patients and documentation evidencing the Investigator's qualifications should be submitted to the IRB/IEC for ethical review and approval according to local regulations, prior to the study start. The written approval should identify all documents reviewed by name and version.

Any changes to the protocol must be approved by the Sponsor in writing unless the change is proposed to assure safety of the patient. In the non-emergent setting, following agreement on the proposed changes, an amendment to the protocol will be submitted by the Sponsor to the IRB for approval prior to implementation of the change. Any change made emergently must be documented in the patient's medical record.

If required by legislation or the IRB/IEC, the Investigator must submit to the IRB/IEC:

- Information on serious or unexpected AEs as soon as possible;
- Periodic reports on the progress of the study.

14.7 Closure of the Study

The Sponsor, its authorized representative, or the Investigator has the right to close this study at any time. The IRB/IEC must be informed, if required by legislation. Should the study be closed prematurely, all unused SL-401 will be reconciled with dispensing records, documented, and, if directed by the Sponsor, destroyed at the study site after completion of accountability by the site monitor.

14.8 Record Retention

The Sponsor will maintain copies of correspondences, records of shipment and disposition of study drug, adverse effects, and other records related to the clinical study and the signed Investigator agreements. Patient records must be retained even if the patient has died.

Study documents must be retained by the Investigator for a minimum of 2 years after the last approval of a marketing application in an ICH region and until there are no pending or contemplated marketing applications in an ICH region or at least 2 years have elapsed since the formal discontinuation of clinical development of the investigational product. These documents should be retained for a longer period, however, if required by the applicable regulatory requirements or by an agreement with the Sponsor. It is the responsibility of the Sponsor to inform the Investigator when storage of these documents is no longer required. The Investigator should contact the Sponsor if the site's archiving arrangements change at any time.

14.9 Liability and Insurance

Liability and insurance provisions for this study are provided in the Investigator's contract with Stemline.

14.10 Financial Disclosure

Prior to study initiation the Investigator will be asked to sign a clinical trial agreement. All Investigators will be required to sign a Financial Disclosure Form in accordance with 21 CFR Part 54; Financial Disclosure by Clinical Investigators.

14.11 Study Monitoring and Auditing

All aspects of the study will be carefully monitored by the Sponsor or its designee for compliance to applicable government regulations with respect to current good clinical practice and current standard operating procedures. Monitoring functions will be performed in compliance with 21CFR§812.43(d) and 21CFR§812.46. Direct access to the on-site study documentation and medical records must be ensured by the Investigator.

14.11.1 Study Monitoring and Source Data Verification

The Investigator is responsible for the validity of all data collected at the site and must accept the various monitoring procedures employed by the Sponsor. The purpose of monitoring is to verify the rights and well-being of human patients are protected; that study data are accurate, complete, and verifiable with source data; that the study is conducted in compliance with the protocol, GCP and the applicable regulatory requirements.

Sites will be monitored to identify and reconcile any differences between the completed eCRFs and medical records, and review source documents for accuracy, completeness, and legibility. The monitor will review completed data forms and study documentation for accuracy, completeness, and protocol compliance. In addition, the Sponsor will evaluate any protocol deviations and take corrective action as necessary.

The Sponsor will review significant new information, including unanticipated AEs and ensure that such information is provided to all reviewing IRBs. This information will also be provided to the FDA, other regulatory authorities, and Investigators worldwide in accordance with local regulations. The monitor's responsibilities include site visits, review of eCRFs, source documents and results, and ensuring clear communication between Investigators and the Sponsor.

The monitor will query any missing or spurious data with the Investigator, which should be resolved in a timely manner. A monitoring log will be maintained recording each visit, the reason for the visit, the monitor's signature, and Investigator's or designee's confirmation signature.

14.11.2 Study Documentation

The Investigator must provide the Sponsor with the following documents prior to enrollment and maintain the accuracy of these documents throughout the course of the study.

- Completed and signed Form 1572.
- All applicable country-specific regulatory forms.
- Current signed and dated curricula vitae for the Investigator, sub-investigators, and other individuals having significant Investigator responsibility who are listed on the Form 1572 or equivalent, or the clinical study information form.
- Copy of the current medical license of the principal Investigator, any sub-investigators and any other individuals having significant responsibility as listed in the Form 1572.
- A financial disclosure form for the Principal Investigator and any other persons listed in the Form 1572.
- Copy of the IRB/IEC approval letter for the protocol and informed consent. All advertising, recruitment, and other written information provided to the patient must be approved by the IRB/IEC. Written assurance of continuing approval (at least annually) as well as a copy of the annual progress report submitted to the IRB/IEC must also be provided to the Sponsor.
- Copy of the IRB/IEC-approved informed consent document.
- A list of the IRB/IEC members or a FWA/DHHS number.
- Copy of the protocol sign-off page signed by the Investigator.
- Fully executed Clinical Trial Agreement including budget.
- A written document containing the name, location, certification number, and date of certification of each laboratory to be used for laboratory assays and those of other facilities conducting tests. This document should be returned along with the laboratory director's curricula vitae and active medical license. A list of normal laboratory values

and units of measure for all laboratory tests required by the protocol is to be provided.

The sites will also be asked to maintain a Delegation of Authority Log, pharmacy logs, temperature logs, patient identification log and monitoring visit logs during this study.

14.11.3 Site Audits

For the purpose of compliance with Good Clinical Practices (GCP) and regulatory agency guidelines, it may be necessary for Sponsor authorized Quality Assurance personnel and/or authorized personnel from a regulatory agency to conduct an audit/inspection of an Investigational site. These site reviews may be planned or spontaneous and occur at any stage during the study. The purpose of an audit is to assess the quality of data with regard to accuracy, adequacy, and consistency, and to assure that studies are in accordance with GCP, protocol, and regulatory agency guidelines.

The Investigator should promptly notify the Sponsor or its authorized representative of any audits by any regulatory authorities and promptly forward copies of any audit reports received to the Sponsor or its authorized representative.

Electronic data systems will be in accordance with applicable aspects of 21 CFR Part 11, ICH Guidelines, GCP, and HIPAA.

14.12 Documentation and Use of Study Findings

14.12.1 Documentation of Study Findings

Source documentation will be maintained to document the treatment and study course of a patient and to substantiate the integrity of the study data submitted for review to regulatory agencies. Source documentation for Stemline studies will include, but not be limited to, worksheets, hospital and/or clinic or office records documenting patient visits including study and other treatments or procedures, medical history and physical examination information, laboratory and special assessments results, drug accountability records, and medical consultations (as applicable).

Laboratory and diagnostic reports including but not limited to: local laboratory hematology and chemistry results, bone marrow biopsy reports, bone marrow aspirate reports, photographs (de-identified), ECHO readings, and MUGA readings may be collected by the study monitor during the course of the study. Every effort should be made by the site to de-identify personal patient information from these reports and replace the information with the patient's study identification number.

14.12.2 Use of Study Findings

All information concerning the product, as well as any matter concerning the operations of the Sponsor, such as clinical indications for the drug, its formula, methods of manufacture, and other scientific data relating to it, that have been provided by the Sponsor and are unpublished, are confidential and must remain the sole property of the Sponsor. The Investigator will agree to use the information only for the purposes of carrying out this study and for no other purpose unless

prior written permission from the Sponsor is obtained. The Sponsor has full ownership of the eCRFs completed as part of the study.

All publications and presentations of the results of the Study are governed by the applicable provisions of the Clinical Trial Agreement between the Sponsor and the institution. By signing the study protocol, the Investigator agrees that the results of the study may be used for the purposes of national and international registration, publication, and information for medical and pharmaceutical professionals by the Sponsor. If necessary, the authorities will be notified of the Investigator's name, address, qualifications, and extent of involvement in the study. The Investigator may not publish or present any information on this study without the express written approval of the Sponsor. Additionally, the Sponsor may, for any reason, withhold approval for publication or presentation. If the Investigator is to be an author of a publication manuscript prepared by the Sponsor, the Sponsor will allow the Investigator 30 days for full review of the manuscript before publication. Such manuscript or materials should be provided for Sponsor review only after the final database is available.

15 References

16.1 Appendix A. Tumor Response Criteria for Patients with AML

Response	Location	Criteria
Complete Remission (CR)	Marrow	
 Normalization of blast percentage ($\leq 5\%$) No detectable Auer rods
	Peripheral Blood	
 Normalization neutrophil count ($\geq 1,000/\mu\text{L}$) and platelet count ($\geq 100,000/\mu\text{L}$) Absence of leukemic blasts
	Extramedullary	
 No extramedullary disease (CNS or soft tissue)
CR with incomplete blood count recovery (CRi)	Marrow	
 Normalization of blast percentage ($\leq 5\%$)
	Peripheral Blood	
 Incomplete recovery of neutrophil and/or platelet count Absence of leukemic blasts
	Extramedullary	
 No extramedullary disease (CNS or soft tissue)
Partial Remission (PR)	Marrow	
 Decrease by $\geq 50\%$ in blast percentage to 5 - 25% or to $\leq 5\%$ with Auer rods present
	Peripheral Blood	
 Normalization neutrophil count ($\geq 1,000/\mu\text{L}$) and platelet count ($\geq 100,000/\mu\text{L}$)
Stable Disease (SD)		
 Failure to achieve at least a PR, but no evidence of progression for at least 8 weeks
Relapse after CR/CRi	Marrow	
 Blast percentage $> 5\%$ (if no peripheral blasts, then confirmation aspirate required ≥ 1 week later)
Relapse after PR	Marrow	
 Blast percentage $\geq 25\%$ (if no peripheral blasts, then confirmation aspirate required ≥ 1 week later)
Progressive Disease (PD)	Marrow	
 $\geq 50\%$ increase in blasts from baseline
	Peripheral Blood	
One or more of the following:
 
 $\geq 50\%$ decrease from peak remission levels in platelets or granulocytes; Reduction in hemoglobin concentration by at least 2 g/dL; Transfusion dependence

Source: [Cheson BD, Bennett JM, Kopecky KJ, et al.](#) Revised recommendations of the international working group for diagnosis, standardization of response criteria, treatment outcomes, and reporting standards for therapeutic trials in acute myeloid leukemia. *J Clin Oncol* 2003;21:4642-4649.

16.2 Appendix B. Tumor Response Criteria for Patients with BPDCN

Response	Location	Criteria
Complete Response (CR)	Marrow ^b	
 Normalization of blast percentage ($\leq 5\%$) ^b
	Peripheral Blood	
 Normalization of neutrophil count ($\geq 1,000/\mu\text{L}$) and platelet count ($\geq 100,000/\mu\text{L}$) Absence of leukemic blasts
	Skin ^a	
 100% clearance of all skin lesions from baseline; no new lesions in patients without lesions at baseline^a
	Nodal Masses	
 Regression to normal size on CT
	Spleen, Liver	
 Not palpable, nodules disappeared
CR with incomplete blood count recovery (CRi)	Marrow ^b	
 Normalization of blast percentage ($\leq 5\%$) ^b
	Peripheral Blood	
 Incomplete recovery of neutrophil and/or platelet count Absence of leukemic blasts
	Skin ^a	
 100% clearance of all skin lesions from baseline; no new lesions in patients without lesions at baseline^a
	Nodal Masses	
 Regression to normal size on CT
	Spleen, Liver	
 Not palpable, nodules disappeared
CR [clinical] with minimal residual skin abnormality (CRc)	Marrow ^b	
 Normalization of blast percentage ($\leq 5\%$) ^b
	Peripheral Blood	
 Normalization of neutrophil count ($\geq 1,000/\mu\text{L}$) and platelet count ($\geq 100,000/\mu\text{L}$) Absence of leukemic blasts
	Skin ^a	
 Marked clearance of all skin lesions from baseline; residual hyperpigmentation or abnormality with BPDCN identified on biopsy (or no biopsy performed) ^a
	Nodal Masses	
 Regression to normal size on CT
	Spleen, Liver	
 Not palpable, nodules disappeared
Partial Response (PR)	Marrow ^b	
 Decrease by $\geq 50\%$ in blast percentage to 5 – 25% ^b
	Peripheral Blood	
 Normalization of neutrophil count ($\geq 1,000/\mu\text{L}$) and platelet count ($\geq 100,000/\mu\text{L}$)
	Skin ^a	
 50% – $<100\%$ clearance of all skin lesions from baseline; no new lesions in patients without lesions at baseline^a
	Nodal Masses	
 $\geq 50\%$ decrease in SPD of up to 6 largest dominant masses; no increase in size of other nodes
	Spleen, Liver	
 $\geq 50\%$ decrease in SPD of nodules (for single nodule in greatest transverse diameter); no increase in size of liver or spleen
Stable Disease (SD)		
 Failure to achieve at least a PR, but no evidence of progression for at least 8 weeks
Relapse after CR/CRi/CRc	Marrow ^b	
 Blast percentage $>5\%$ (if no peripheral blasts, then confirmation aspirate required ≥ 1 week later) ^b
	Peripheral Blood	
 Presence of leukemic blasts
	Skin ^a	
 Increase in skin score greater than the sum of nadir plus 50% baseline score^a
	Nodal Masses	
 Appearance of a new lesion(s) >1.5 cm in any axis, $\geq 50\%$ increase from nadir in SPD of more than one node, or $\geq 50\%$ increase from nadir in longest diameter of a previously identified node >1 cm in short axis
	Spleen, Liver	
 $>50\%$ increase from nadir in the SPD of any previous lesions

Relapse after PR ^c	Marrow ^b	
 Blast percentage $\geq 25\%$ (if no peripheral blasts, then confirmation aspirate required ≥ 1 week later)^b
	Skin ^a	
 Increase in skin score greater than the sum of nadir plus 50% baseline score^a
	Nodal Masses	
 Appearance of a new lesion(s) > 1.5 cm in any axis, $\geq 50\%$ increase from nadir in SPD of more than one node, or $\geq 50\%$ increase from nadir in longest diameter of a previously identified node > 1 cm in short axis
	Spleen, Liver	
 $> 50\%$ increase from nadir in the SPD of any previous lesions
Progressive Disease (PD) ^c	Marrow ^b	
 $\geq 50\%$ increase in blasts from baseline (and blast percentage $> 5\%$)^b
	Peripheral Blood	
 One or more of the following: 
 $\geq 50\%$ decrease from peak remission levels in platelets or granulocytes; Reduction in hemoglobin concentration by at least 2 g/dL; Transfusion dependence
	Skin ^a	
 One or more of the following: 
 $\geq 25\%$ increase in skin disease from baseline^a Any new tumors in patients without tumors at baseline
	Nodal Masses	
 Appearance of a new lesion(s) > 1.5 cm in any axis, $\geq 50\%$ increase from nadir in SPD of more than one node, or $\geq 50\%$ increase from nadir in longest diameter of a previously identified node > 1 cm in short axis
	Spleen, Liver	
 $> 50\%$ increase from nadir in the SPD of any previous lesions

Source: [Cheson BD, Pfistner B, Juweid ME, et al.](#) The International Harmonization Project on Lymphoma. Revised response criteria for malignant lymphoma. *J Clin Oncol* 2007;25:579-586.

Abbreviations: CT, computed tomography; SPD, sum of the product of the diameters.

All parameters detailed above (including bone marrow, blood, skin [including mSWAT quantification], lymph nodes and viscera) are to be assessed both at baseline and stipulated subsequent timepoints. Responses are determined via comparison to baseline values (or post-treatment nadir values as stipulated in the above table).

^a The percentage of clearance or increase in skin disease is calculated using the Modified Severity Weighted Assessment Tool (mSWAT), which is provided in [Section 16.3/Appendix C](#). Detailed guidance and examples regarding the calculation of an mSWAT assessment based on the size and nature of a patient's skin lesions are provided in a separate document.

^b In settings in which there is a change in the blast population on bone marrow evaluation by means of flow cytometry or other molecular methodology without a similar degree of change in the morphologic blast percentage, the morphologic percentage should be utilized to determine response/progression; however the findings from flow cytometry (or other molecular methodology) should be recorded as part of the study record.

^c In settings in which there is preliminary but not conclusive evidence of disease progression (i.e., new skin lesions of indeterminate etiology, new lymph nodes ≤ 1.5 cm, modest increase in bone marrow blast percentage subsequent to an initial marked reduction, appearance of new blast population on bone marrow evaluation by means of flow cytometry or other molecular methodology without increase in blast percentage consistent with PD), additional SL-401 cycles may be administered, provided that the Investigator documents that the evidence of potential disease progression is inconclusive and that the overall risk/benefit assessment favors additional investigational therapy. Additional SL-401 may also be administered in situations of mixed response BPDCN in which response/progression is not consistent between a given patient's disease sites, provided that the Investigator documents that the overall risk/benefit assessment favors additional investigational therapy. In such situations, it is essential that relevant findings and assessments are documented, and that areas of potential disease progression are followed closely on subsequent assessments.

16.3 Appendix C. Modified Severity Weighted Assessment Tool

Body Region	%BSA in Body Region	Assessment of Involvement in Patient's Skin		
		Patch ^a	Plaque ^b	Tumor ^c
Head	7			
Neck	2			
Anterior trunk	13			
Arms	8			
Forearms	6			
Hands	5			
Posterior trunk	13			
Buttocks	5			
Thighs	19			
Legs	14			
Feet	7			
Groin	1			
Subtotal of weighted BSA				
Weighting factor		× 1	× 2	× 4
Weighted subtotal				

Note: mSWAT score equals summation of weighted subtotals.

Abbreviations: BSA, body surface area; mSWAT, modified Severity Weighted Assessment Tool. Detailed guidance and examples regarding the calculation of an mSWAT assessment based on the size and nature of a patient's skin lesions are provided in a separate document.

^aAny size lesion without induration or significant elevation above the surrounding unininvolved skin; poikiloderma may be present.

^bAny size lesion that is elevated or indurated; crusting, ulceration, or poikiloderma may be present.

^cAny solid or nodular lesion ≥ 1 cm in diameter with evidence of deep infiltration in the skin and/or vertical growth.

16.4 Appendix D. ECOG Performance Status

Grade	Description
0	ABLE TO CARRY OUT ALL NORMAL ACTIVITIES WITHOUT RESTRICTION.
1	RESTRICTED IN PHYSICALLY STRENUOUS ACTIVITY BUT AMBULATORY AND ABLE TO CARRY OUT WORK OF A LIGHT OR SEDENTARY NATURE.
2	AMBULATORY AND CAPABLE OF ALL SELF-CARE BUT UNABLE TO CARRY OUT ANY WORK ACTIVITIES: UP AND ABOUT MORE THAN 50% OF WAKING HOURS.
3	CAPABLE OF LIMITED SELF-CARE; CONFINED TO BED OR CHAIR MORE THAN 50% OF WAKING HOURS.
4	COMPLETELY DISABLED; CANNOT CARRY ON SELF-CARE; TOTALLY CONFINED TO BED OR CHAIR.

16.5 Appendix E. CLS Management Guidance

Time of Presentation	CLS Sign/Symptom	Recommended Action	ELZONRIS Dosing Management
Prior to first dose of ELZONRIS in cycle 1	Serum albumin < 3.2 g/dL	Administer ELZONRIS when serum albumin \geq 3.2 g/dL.	
During ELZONRIS dosing	Serum albumin < 3.5 g/dL		Interrupt ELZONRIS dosing until the relevant CLS sign/symptom has resolved ¹ .
	Serum albumin reduced by \geq 0.5 g/dL from the albumin value measured prior to ELZONRIS dosing initiation of the current cycle	Administer 25g intravenous albumin (q12h or more frequently as practical) until serum albumin is \geq 3.5 g/dL AND not more than 0.5 g/dL lower than the value measured prior to dosing initiation of the current cycle.	
	A predose body weight that is increased by \geq 1.5 kg over the previous day's predose weight	Administer 25g intravenous albumin (q12h or more frequently as practical), and manage fluid status as indicated clinically (e.g., generally with intravenous fluids and vasopressors if hypotensive and with diuretics if normotensive or hypertensive), until body weight increase has resolved (i.e. the increase is no longer \geq 1.5 kg greater than the previous day's predose weight).	
	Edema, fluid overload and/or hypotension	Administer 25g intravenous albumin (q12h, or more frequently as practical) until serum albumin is \geq 3.5 g/dL. Administer 1 mg/kg of methylprednisolone (or an equivalent) per day, until resolution of CLS sign/symptom or as indicated clinically. Aggressive management of fluid status and hypotension if present, which could include intravenous fluids and/or diuretics or other blood pressure management, until resolution of CLS sign/symptom or as clinically indicated.	

¹ ELZONRIS administration may resume in the same cycle if all CLS signs/symptoms have resolved and the patient did not require measures to treat hemodynamic instability. ELZONRIS administration should be held for the remainder of the cycle if CLS signs/symptoms have not resolved or the patient required measures to treat hemodynamic instability (e.g. required administration of intravenous fluids and/or vasopressors to treat hypotension) (even if resolved), and ELZONRIS administration may only resume in the next cycle if all CLS signs/symptoms have resolved, and the patient is hemodynamically stable.

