Patients who benefit from treatment and do not have evidence of clinically significant progressive disease may receive repeated cycles of SL-401 even if a response, in the judgment of the Investigator, is not attained. Patients should continue to receive SL-401 as long as they may be benefiting from treatment, according to the Investigator; no maximum duration of therapy has been set.

Patients will receive the following premedications approximately 60 minutes before each SL-401 infusion:

- Acetaminophen 650 mg (or equivalent dose of paracetamol) orally (PO)
- Diphenhydramine 50 mg IV (or equivalent dose of another H1-histamine antagonist)
- Methylprednisolone 50 mg IV (or an equivalent dose of another corticosteroid)
- Ranitidine 50 mg IV (or an equivalent dosage of another H₂-histamine antagonist)

During the dosing period for each cycle, individual SL-401 infusions may be delayed to allow for toxicity resolution, as detailed in [Section 7.5.5](#).

During the first cycle, patients will receive a starting dose according to their dosing cohort in Stage 1, or the dose carried into Stages 2-4. Potential dose modifications for subsequent cycles relative to the prior cycle dose will be based on the severity and resolution of toxicities. Dose reductions should be discussed with the medical monitor on a case by case basis.

Procedures During Dosing Period:

During each cycle, testing and procedures that may result in withholding of a scheduled SL-401 infusion, largely based on unresolved manifestations of fluid retention and/or other relevant acute toxicities during daily dosing, are described in [Table 5](#), [Table 6](#), [Table 7](#), and [Table 8](#) in Section 9.8.

Withhold SL-401 infusion if any of the following occur:

- Body temperature $\geq 38^{\circ}\text{C}$
- Heart rate ≥ 130 or ≤ 40 bpm
- Systolic blood pressure (BP) ≥ 160 or ≤ 80 mmHg
- Serum creatinine > 1.8 mg/dL (159 $\mu\text{mol/L}$)
- Serum albumin
 - In settings in which albumin is reduced to 3.0-3.5 g/dL (30-35 g/L) or by ≥ 0.5 g/dL (5 g/L) below the level at the start of the cycle, withhold SL-401 infusion and administer albumin 25 g IV daily or every 12 hours as clinically feasible until serum

albumin is both ≥ 3.5 g/dL and not reduced by ≥ 0.5 g/dL from the level at the start of the cycle prior to resuming treatment with SL-401 in the same cycle.

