- In settings in which albumin is reduced to <3.0 g/dL (30 g/L) or by more than 1.0 g/dL (10 g/L) below the level at the start of the cycle (i.e., from 4.3 g/dL to 3.2 g/dL), withhold SL-401 infusions for the duration of that particular cycle. Albumin should be administered until the albumin level is at least above 3.5g/dL. Consultation with the Medical Monitor is advised.
- Dosing in the next cycle may resume if albumin remains at 3.5 g/dL without additional albumin infusions.
- AST >5 times the ULN or ALT >5 times the ULN (SL-401 will be withheld for remainder of study cycle)
- Increase in body weight by ≥ 1.5 kg over pre-treatment weight on the prior treatment day.

Refer to [Section 7.5.5](#) for dose modifications/delays. Management procedures for capillary leak syndrome (CLS) and associated symptoms are provided in [Section 16.5, Appendix E](#).

Concomitant Medications:

Recommended Medications Per Institutional Guidelines/Practices:

It is recommended that patients receive the following types of prophylactic therapies/regimens per institutional guidelines/practices:

- Antibacterial: ciprofloxacin, levofloxacin, or an equivalent antibiotic
- Antifungal: fluconazole, voriconazole, or an equivalent antifungal
- Antiviral: acyclovir, valacyclovir or an equivalent antiviral

Allowed Medications/Therapies:

All patients may receive supportive care measures as clinically indicated, including prophylactic antibiotics, antihistamines, antiemetics, albumin, fluids (hydration), and supportive measures. Patients may receive growth factor support and/or blood product transfusions as per the discretion of their physician.

Albumin 25 g IV daily should be administered if serum albumin is between 3.0-3.5 g/dL (30-35 g/L) on days that dosing occurs or if it is <3.0 g/dL (30 g/L) on days when treatment has been withheld or in the immediate post-treatment period. The Investigator has discretion with regard to frequency of administration.

Prohibited Medications/Therapies:

An enrolled patient may not receive investigational or approved anticancer or anti-leukemia agents, including cytotoxic chemotherapy agents, hypomethylating agents (5-azacytidine, decitabine or others), or anticancer tyrosine kinase inhibitors (including imatinib, ruxolitinib, sorafenib and others) or therapeutic monoclonal antibodies. Hydroxyurea may be administered (however its use should be discussed with the Medical Monitor).

Assessments:

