7.5.5 Dose Delays/Modifications and Management Procedures for Toxicities Associated with SL-401

During the dosing period for each cycle, individual SL-401 infusions may be delayed to allow for toxicity resolution. Details are presented in [Table 4](#).

Monitor vital signs and check albumin, transaminases, and creatinine prior to preparing each dose of ELZONRIS.

Table 4: Recommended ELZONRIS Dose Modifications

Parameter	Severity Criteria	Dose Modification
Serum albumin	Serum albumin < 3.5 g/dL or reduced \geq 0.5 g/dL from value measured prior to initiation of the current cycle	See CLS Management Guidelines (Appendix E)
Body weight	Body weight increase \geq 1.5 kg over pretreatment weight on prior treatment day	See CLS Management Guidelines (Appendix E)
Aspartate aminotransferase (AST) or alanine aminotransferase (ALT)	ALT or AST increase $>$ 5 times the upper limit of normal	Withhold SL-401 until transaminase elevations are \leq 2.5 times the upper limit of normal.
Serum creatinine	Serum creatinine $>$ 1.8 mg/dL (159 micromol/L) or creatinine clearance $<$ 60 mL/minute	Withhold SL-401 until serum creatinine resolves to \leq 1.8 mg/dL (159 micromol/L) or creatinine clearance \geq 60 mL/minute.
Systolic blood pressure	Systolic blood pressure \geq 160 mmHg or \leq 80 mmHg	Withhold SL-401 until systolic blood pressure is $<$ 160 mmHg or $>$ 80 mmHg.
Heart rate	Heart rate \geq 130 bpm or \leq 40 bpm	Withhold SL-401 until heart rate is $<$ 130 bpm or $>$ 40 bpm.
Body temperature	Body temperature \geq 38°C	Withhold SL-401 until body temperature is $<$ 38°C.
Hypersensitivity reactions	Mild or moderate	Withhold SL-401 until resolution of any mild or moderate hypersensitivity reaction. Resume ELZONRIS at the same infusion rate.
	Severe or life-threatening	Discontinue SL-401 permanently.

Dose reductions should be discussed with the medical monitor on a case by case basis.

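### Appendix E judges the 1.5 kg weight gain against the previous day, the Synopsis and Table 4 against the prior treatment day; after a held infusion a weight plateau can read as resolved

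*Protocol*

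**What the plan says.** Three places in the protocol deal with weight gain during dosing.

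- **Synopsis, Procedures During Dosing Period.** The list opens with "Withhold SL-401 infusion if any of the following occur" and includes a gain of at least "1.5 kg over pre-treatment weight on the prior treatment day". It then refers to Section 7.5.5 for delays and to Appendix E for managing CLS.
- **Section 7.5.5, Table 4.** The criterion is a gain of at least "1.5 kg over pretreatment weight on prior treatment day". The action column gives no limit of its own for weight and sends the reader to Appendix E.
- **Section 16.5, Appendix E.** The trigger is a predose weight up by at least "1.5 kg over the previous day's predose weight". Albumin and fluid management run until the increase is no longer at least "1.5 kg greater than the previous day's predose weight". Dosing is interrupted until the sign has resolved. Footnote 1 says that dosing "may resume in the same cycle if all CLS signs/symptoms have resolved", provided no measures for hemodynamic instability were needed.

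Section 9.3.1 has the pre-treatment weight recorded on every day with a planned infusion. Table 7 footnote (n) allows infusions to be delayed, with all of them completed within 10 days.

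**The concern.** The previous day and the prior treatment day are the same day only while no infusion is missed. Once an infusion is held, the previous day is a held day, and its weight may already contain the gain that caused the hold. A patient who has lost none of that weight then shows no increase on Appendix E's test.

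The row above in Appendix E avoids this. A fall in albumin is measured "from the albumin value measured prior to ELZONRIS dosing initiation of the current cycle", a fixed reference, so a plateau at a low value cannot pass as recovery. The weight row has no such anchor.

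Section 3.8 names CLS as the principal dose-limiting toxicity in both Study 50047 and this study, and lists withholding treatment for weight increases among the added precautions. A site should not have to choose between two reference weights when applying that precaution.

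**Working it through.** The documents give no weight data and no frequency of holds, so all weights below are assumed for illustration. The 1.5 kg threshold comes from the three places cited.

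Let D be the weight on the last dosed day, H the weight on the previous day (held), and W the weight today, before a possible dose.

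1. Synopsis and Table 4: trigger met if W − D ≥ 1.5.
2. Appendix E: sign present if W − H ≥ 1.5, and resolved otherwise.
3. With no held day, H and D are the same weight and the two tests are identical.
4. After a held day, the Synopsis/Table 4 trigger is met while Appendix E reads as resolved when D + 1.5 ≤ W < H + 1.5. The width of this range is H − D, so the more weight was gained by the held day, the wider the disagreement. (If H is below D, the disagreement runs the other way and Appendix E is the stricter test.)

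With D = 70.0 and H = 72.0 the range is 71.5 ≤ W < 73.5 kg:

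| W (kg) | W − D | W − H | Synopsis/Table 4 | Appendix E |
|---|---|---|---|---|
| 71.4 | +1.4 | −0.6 | not met | resolved (agree) |
| 72.0 | +2.0 | 0 | met | resolved (**disagree**) |
| 73.5 | +3.5 | +1.5 | met | present (agree) |

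A smaller gain shows the same thing. For 70.0 dosed, 71.6 held and 71.6 today, the gains are +1.6 against 0.

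The trigger can differ too. Suppose the middle day is held for another reason and the weights are 70.0 dosed, 71.0 held and 72.0 today. The gain is 72.0 − 70.0 = +2.0 from the dosed day and 72.0 − 71.0 = +1.0 from the previous day. The Synopsis and Table 4 catch this patient; Appendix E's own weight row does not.

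With the prior treatment day as the reference in all three places, the 70.0 / 72.0 / 72.0 patient shows +2.0 kg under every rule and stays on hold until weight falls below 71.5 kg.

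Reach among new entrants is small. The current text cites the approval of 21 December 2018, and SAP Section 1.1 ends Stage 4 enrollment on 7 January 2019: 10 + 7 = 17 days at most. Treatment has no maximum duration (Section 7.5.2), so patients still receiving cycles were also covered.

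**The case against.** The strongest reply is that no patient is dosed wrongly if the whole protocol is followed. In the 70.0 / 72.0 / 72.0 case the Synopsis hold still applies, and Table 4's criterion is met again and sends the patient back to Appendix E. Appendix E has a separate row for edema, fluid overload or hypotension, which would catch clinically recognised fluid retention. Footnote 1 requires every CLS sign to have resolved, and it permits dosing rather than ordering it. Section 7.5.5 also tells sites to "check albumin, transaminases, and creatinine prior to preparing each dose of ELZONRIS", and the vital-sign limits remain. All of this stands, and it confines the gap to weight gain as the only remaining sign.

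The wording can also be harmonised. The increase that must resolve could mean the one that set off the row; predose could be taken to imply a day on which a dose was given; and prior treatment day could loosely mean the preceding day of the dosing period. These are fair readings and they lower confidence, but the text states none of them, and Section 9.3.1 produces a pre-treatment weight on held days as well.

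A reader might infer that two places give opposite rules on when albumin and fluid management may stop. The documents do not support that. For weight, the Synopsis and Table 4 contain a trigger only; the stop rule exists in Appendix E alone. The conflict is between a trigger that is still met and a resolution test that reads as passed.

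A reader might also see a conflict when the first infusion of a cycle is held and weight then rises and levels off. That would compare Appendix E with a cycle-start weight, which none of the three weight rules uses.

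**Conclusion.** The point holds as a minor safety-rule correction, with moderate confidence. Appendix E is the only place that says when a weight-triggered hold has resolved, and on its plain wording it can class an unresolved gain as resolved after a held day. With the assumed 70.0 and 72.0 kg, this happens across a 2.0 kg range of weights today.

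It would go too far to conclude that the protocol directs sites to dose patients who are still retaining fluid: the Synopsis hold is mandatory and the other signs and limits remain in force. How often weight gain would be the sole remaining sign cannot be estimated from the documents. The conclusion rests on reading the previous day as the preceding calendar day, with weight recorded on it even though the infusion was held. Efficacy analyses and the SAP's CLS derivations are not affected.

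**What to change.** In both weight phrases of Appendix E, replace the previous-day reference with the pre-treatment weight on the prior treatment day, defined as the last day SL-401 was given in the current cycle. Send sites a short notice; the 70.0 dosed / 72.0 held / 72.0 kg case, still held, would serve as a worked example. Footnote 1 and the SAP need no change.

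Optionally, state that the weight at the start of the cycle applies when no dose has yet been given in it. That fills an unspecified case; it does not correct a conflict between documents.

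The cost is somewhat longer holds and possibly fewer infusions in a cycle. Five infusions in 10 days leave room for at most 10 − 5 = 5 held days, and Table 7 footnote (n) already accepts fewer than five infusions for incipient CLS. Section 3.8 says Amendment 12 modified certain procedures to follow the approved package insert. If this wording came from there, which the documents do not say, Appendix E would become stricter than its source, though no stricter than the Synopsis and Table 4 already are.
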